PROTOCOL COVER SHEET

Immediate Weight-bearing Verses Non-Weight-bearing after Foot & Ankle Surgery: A Prospective Analysis

04/29/2019

PRINCIPAL INVESTIGATOR [name], DPM, FACFAS

CO-INVESTIGATORS [name], DPM [name], DPM, FACFAS THE FOOT & ANKLE INSTITUTE STEEL VALLEY ORTHOPAEDIC AND SPORTS MEDICINE [name] [contact]

Email: [contact]

ABBREVIATIONS AND DEFINITIONS OF TERMS

NWB	Non-weight-bearing
WB	Weight-bearing
AE	Adverse event
SAE	Serious adverse event

ABSTRACT

In recent years, significant attention has been placed on the safety and efficacy of immediate weight-bearing following foot and ankle surgery. Returning patients to their previous activities as quickly as possible following surgery is always in the mind of providers, but the question of when has been difficult to answer.

Objectives:

The primary objective is to assess if immediate weight-bearing following foot and ankle surgery will yield equivalent, if not superior outcomes to the traditional non-weight-bearing post-operative course, while avoiding the undesirable effects commonly experienced during extended periods of non-weight-bearing. This will be determined by serial radiographs and/or other appropriate imaging modalities, physical exams and using patient self-reported pre- and post-operative SF-36 and AOFAS questionnaires.

Study Design:

Prospective, randomized controlled trial.

Setting/Participants:

Patients will be consented from 5 sites West Penn Hospital, Jefferson Regional Hospital, Forbes Regional Hospital, Bethel Park Surgery Center, and Monroeville Surgery Center and the level of care will include both inpatient and outpatient.

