The subjects will be identified/recruited during clinic hours as patients requiring an elective or traumatic foot and ankle surgery. During the clinic hours the primary investigator and/or the co-investigator will obtain full consent from the patient. We will recruit a minimum of 115 participants into each of two study arms, an immediate weight-bearing arm and a non-weight-bearing arm, so 230 participants will be included. Patients will be eligible if they are undergoing elective or traumatic foot and ankle surgery. Exclusion criteria will include any patient less than 18 years of age & over 89, history of foot or ankle surgery on the surgical limb, any degree of diagnosed peripheral neuropathy or peripheral vascular disease, infection, and/or unwillingness to participate at random in one of the two study arms.

Study Interventions and Measures:

We will be assessing the difference in two groups; immediate protected weight-bearing in a CAM walking boot vs strict non-weight-bearing for 6 weeks following foot and ankle surgery. Monitoring will be done by way of clinical follow-up, serial radiographs and/or other appropriate imaging modalities, and patient reported outcomes by way of AOFAS and SF-36 surveys.

Surgical procedures performed on patients included in the study will vary, as will the outcome measures for each procedure. Osseous fusions, including both elective joint fusions and bone healing following trauma, will be assessed by both clinical and radiographic evaluation. Soft tissue procedures, including elective stabilization and traumatic soft tissue repairs, will be assessed clinically and with imaging modalities

deemed appropriate. Complications during the perioperative and post-operative periods, such as non-union, infection, etc. will be included in the outcomes. All participants will also complete AOFAS and SF-36 surveys in the pre-operative and post-operative periods. We will also include return to work, activity, sport, etc. where appropriate.

Study Phase	Screening	Surgery	Post-op 2-3 w	Post-op 6-8 w	Post-op 3 m	Post-op 6 m	Post-op 1 yr	Post-op 2 yr	Unscheduled Visits
Visit Number	1		2	3	4	5	6	7	
Informed									
Informed Consent/Assent	x								
Review Inclusion/Exclusion									
Criteria	х								
Randomization	x								
Demographics/PMH	x								
Physical Examination	x		x	x	x	x	x	x	x
Adverse Event Assessment			x	x	x	x	x	x	x
Radiographs/Imagining	х		x	x	x	x	x	x	x
Complete AOFAS/SF- 36 survey	x			x	x		x	x	

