6.4 Statistical Methods

6.4.1 Analysis of Primary Outcome of Interest

All analysis will begin with assessment of the normality of continuous variables using the Kolmogorov-Smirnov test. Normally distributed continuous variables will be reported as means and standard deviations; non-normally distributed data as median and interguartile range. Categorical data will be reported as counts and percentages. The Student's t-test will be used to compare continuous demographic and clinical data between the immediate weight-bearing and non-weight-bearing groups. The chi-square test or Fisher's exact test will be used to compare categorical data between groups. Cronbach's alpha will be used to measure reliability, or internal consistency, of both the Medical Outcomes Study 36-Item Short Form Health Survey (SF-36) and the AOFAS Ankle-Hindfoot Scale survey (AOFAS). Spearman's rank correlation coefficient will be used to assess the relationship between the physical and mental component scores and the eight subdomain scores from the SF-36 and the pain, function and alignment scores of the AOFAS. SF-36 scores and AOFAS scores will be adjusted for patient age, gender, BMI and presence of diabetes mellitus. Nonparametric tests will be used when data breaks the normality assumption. A value of p<.05 on twotailed testing will be considered statistically significant. Statistical analysis will be performed using IBM-SPSS Statistics, version 24.0 (IBM-SPSS Inc., Armonk, NY). Using one-way repeated measures analysis of variance (ANOVA), differences over time in radiographic and advanced imaging parameters will be assessed separately for the immediate weight-bearing and non-weight-bearing groups. Two-way repeated measures ANOVA will be used to assess differences over time in these parameters between the two groups. Tukey's test or Dunn's procedure will be used for post-hoc pairwise comparisons, as indicated.

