Due to the potential small sample sizes associated with the various orthopaedic procedures included in this study, the primary analysis will focus on the comparison of the immediate weight-bearing and non-weight bearing groups. Any analyses associated with an individual orthopaedic procedure will be considered exploratory. Finally, the data will not be adjusted for the center where the procedure was performed.

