6.5 Sample Size and Power

The study power calculation is based on the primary endpoints.

Assuming the American Orthopaedic Foot and Ankle Society (AOFAS) Ankle-Hindfoot Scale score and the SF-36 Health Survey Score (as it pertains to the patient's foot/ankle) are normally distributed in the immediate weight-bearing and non-weight-bearing groups and using an independent-samples t-test with a .05 two-sided significance level, and (absent any prior study results) assuming a "medium" effect size of Cohen's d = 0.40, 200 evaluable patients (100 patients in each group) would give you a power of 80% to detect a true difference in means on the questionnaires, if present. Fifteen patients will be added to each group for the potential of loss to follow-up. Final sample size is 230 patients (115 patients in each group). Sample size was calculated using an a-priori sample size calculator for Student t-tests (2017) available from http://www.danielsoper.com.

¹ "Effect size" is a statistical expression of the magnitude of the difference between two groups (Portney and Watkins, 2000). The standardized mean effect, one type of effect size, expresses the mean difference between two groups in standard deviation units. This is

typically reported as Cohen's "d." Interpretation of effect size depends on the research question. Cohen (1988) defines his effect sizes as: 8 = large (8/10 of a standard deviation unit). 5 = moderate (1/2 of a standard deviation). 2 = small (1/5 of a standard deviation). I would recommend using the "medium" effect size for your project. A medium effect size can range from 0.3 to 0.5.

SAFETY MANAGEMENT

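### The adjusted score comparison omits procedure type and excludes centre without a reason, giving up some precision and some protection against case-mix imbalance

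*Combined protocol and SAP*

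**What the plan says.** Section 6.4.1 commits to covariate adjustment: "SF-36 scores and AOFAS scores will be adjusted for patient age, gender, BMI and presence of diabetes mellitus". Procedure type is not in that list. The section closes by saying that "the data will not be adjusted for the center where the procedure was performed" and gives no reason. Just before that, it makes the pooled comparison of the two arms primary because numbers per procedure may be small, and it labels any single-procedure analysis exploratory.

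The scores are to be analysed by repeated measures ANOVA, with screening as one of the visits. The section does not say which model carries the covariates. Surgical characteristics appear only in a separate logistic regression that looks for predictors of higher scores.

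Elsewhere the plan expects a mixed population. The Abstract says: "Surgical procedures performed on patients included in the study will vary, as will the outcome measures for each procedure". There are five sites, hospitals and surgery centers, and "the level of care will include both inpatient and outpatient". The data form in the Appendix has 21 procedure items by count, from first MPJ fusion to ankle fusion and TAR. Section 3.1 allocates the first patient by coin flip and alternates after that, with no stratification. Section 6.3 and the introduction to the SF-36 form, by contrast, speak of hindfoot fusion only.

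**The concern.** Neither the design nor the analysis deals with procedure or centre. Three features of the plan suggest that procedure bears on the scores:

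- The logistic regression in section 6.4.1 looks for surgical characteristics associated with them.
- Section 2.2 asks whether some procedures suit immediate weight-bearing better.
- The AOFAS Ankle-Hindfoot Scale awards up to 8 of its 100 points for sagittal motion. An ankle fusion affects that item directly, in either arm; a first MPJ fusion does not.

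Spread between procedures that is not modelled stays in the error term of a two-group comparison and lowers power. An uneven case mix between the arms also goes uncorrected. With 200 evaluable patients there are on average 200/21 = 9.5 per listed procedure (4.8 per arm) and 200/5 = 40 per site, so some unevenness is likely.

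**Working it through.** **The plan's own figure.** Section 6.5 bases power on the two primary scores, "using an independent-samples t-test with a .05 two-sided significance level", with d = 0.40, and states that "200 evaluable patients (100 patients in each group) would give you a power of 80" per cent. The noncentrality is 0.40/√(2/100) = 2.828 on 198 df. Exact noncentral-t power is 80.4% at 100 per arm and 79.97% at 99, so the stated figure reproduces. "Fifteen patients will be added to each group for the potential of loss to follow-up": 15/115 = 13.0%, and 100/(1 − 0.130) = 115.

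**Power after adjustment.** Let N = 200 and let k be the number of added covariate terms. R² is the share of score variance that they explain beyond covariates already in the model. The variance of the treatment difference is multiplied by

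f = (1 − R²) × (N − 3)/(N − k − 3),

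and power follows from noncentrality 0.40/√(f × 2/100) on N − 2 − k df. Adjustment pays when R² exceeds k/(N − 3). R² is not in the documents and is assumed over 0 to 0.30. The four-group split of procedures is also an assumption.

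| Added terms | k | Break-even R² | R² = 0 | 0.10 | 0.20 | 0.30 |
|---|---|---|---|---|---|---|
| None (unadjusted) | 0 | – | 80.4% | 80.4% | 80.4% | 80.4% |
| Four procedure groups | 3 | 3/197 = 0.015 | 79.8% | 83.7% | 87.8% | 91.6% |
| Four groups + centre | 7 | 7/197 = 0.036 | 78.9% | 83.0% | 87.1% | 91.0% |
| All 21 procedures separately | 20 | 20/197 = 0.10 | 76.0% | 80.3% | 84.6% | 89.0% |

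Example, seven terms at R² = 0.20: f = 0.80 × 197/190 = 0.829; noncentrality = 2.828/√0.829 = 3.11; power = 87.1%.

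Simulation with 4,000 runs per setting agrees. With four groups, adjusted power was 80%, 84%, 87% and 92% at the same four R² values.

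**Chance imbalance.** If allocation behaves as random, the omitted factors shift the treatment difference with SD √(R² × 2/100), in units of the score SD. The 95% range is ±1.96 times that:

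- R² = 0.10: ±0.09, or 22% of the planned 0.40
- R² = 0.20: ±0.12, or 31%
- R² = 0.30: ±0.15, or 38%

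This variation is already part of the unadjusted standard error. It is not a bias on top of it.

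**Validity.** Simulated type I error, with 21 procedures, was 4.9% unadjusted and 4.8% adjusted at R² = 0.10, and 4.7% and 5.2% at R² = 0.30. Omitting the factors does not inflate it.

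**The case against.** The strongest reply is that this is an efficiency choice of unknown size. The documents give no R², intraclass correlation or between-procedure SD, and under random-like allocation the planned comparison is unbiased on average. That stands, and it limits the point to precision and protection from imbalance.

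Second, the t-test calculation is not the planned analysis. With screening as one of the visits, the group-by-time test of a repeated measures ANOVA already removes stable differences between patients, including stable procedure effects. Only procedure effects that change over time, or a test of the group main effect, would benefit. This also stands: the table follows the basis of section 6.5, and the gain under section 6.4.1 may be smaller.

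Third, section 6.4.1 gives small numbers per procedure as its reason for pooling. That argues against 20 separate terms, which gain only above an R² of about 0.10. It does not argue against a few groups, and it gives no reason for excluding centre.

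Fourth, the data may be incomplete. The legible data form has procedure boxes but no visible field for centre or elective/trauma status, and the abstraction list in section 5.1.1 has neither. Section 7.1.2 records surgery type and operative reports in Epic, so both may be recoverable, but the documents do not show it. The form also allows several procedures per patient, so groups can overlap.

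Finally, section 6.4.1 compares clinical characteristics between the arms. That could reveal an imbalance but would not correct it.

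**Conclusion.** The gap is real and worth closing. It is a cheap improvement and not a flaw that invalidates the trial. On the t-test basis, a few procedure groups, with or without centre, gain about 3 to 11 power points if R² is 0.10 to 0.30. They cost 0.6 points (procedure only) to 1.5 points (with centre) if the factors predict nothing. All of this rests on the assumed R² and on allocation that behaves as random.

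A reader might infer more than the documents support:

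- **Procedure and centre are the strongest predictors available.** Nothing shows this. The pre-operative scores are also collected and may predict more.
- **The precision is free.** It costs degrees of freedom, and with one term per procedure the cost is material.
- **Adjustment would repair the allocation.** After the first coin flip the next arm is predictable, and section 7.4 leaves recruitment to the surgeons' discretion. Covariates cannot correct selection on unrecorded factors.

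How much procedure variation exists depends on which population statement is right: the hindfoot-fusion wording or the mixed list.

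**What to change.** First reconcile section 6.3 and the SF-36 form introduction with the mixed procedure list. Then amend section 6.4.1, before outcomes are examined, as follows:

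1. Compare post-operative SF-36 and AOFAS scores between the arms, adjusting for screening score and a few pre-specified procedure groups as well as age, gender, BMI and diabetes. Name the model.
2. State a rule for assigning a patient with several procedures to a group.
3. Take screening out of the outcome visits in the repeated measures analysis, so that it is not both an outcome level and a covariate.
4. Add centre, with a merging rule for small centres, and elective/trauma status if both can be taken from the operative records. Otherwise, give the reason for leaving them out.
5. Report the comparison without the added covariates as a sensitivity analysis.

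The pooled comparison stays primary, and no new visits or assessments are needed. The cost is SAP wording, possibly some abstraction from existing records, and the degrees of freedom shown above. Each further term, such as screening score, inflates the variance by about 1/197 = 0.5%. Any gain from screening score comes on top and cannot be sized from the documents.

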6.5 Sample Size and Power

The study power calculation is based on the primary endpoints.

Assuming the American Orthopaedic Foot and Ankle Society (AOFAS) Ankle-Hindfoot Scale score and the SF-36 Health Survey Score (as it pertains to the patient's foot/ankle) are normally distributed in the immediate weight-bearing and non-weight-bearing groups and using an independent-samples t-test with a .05 two-sided significance level, and (absent any prior study results) assuming a "medium" effect size of Cohen's d = 0.40, 200 evaluable patients (100 patients in each group) would give you a power of 80% to detect a true difference in means on the questionnaires, if present. Fifteen patients will be added to each group for the potential of loss to follow-up. Final sample size is 230 patients (115 patients in each group). Sample size was calculated using an a-priori sample size calculator for Student t-tests (2017) available from http://www.danielsoper.com.

¹ "Effect size" is a statistical expression of the magnitude of the difference between two groups (Portney and Watkins, 2000). The standardized mean effect, one type of effect size, expresses the mean difference between two groups in standard deviation units. This is

typically reported as Cohen's "d." Interpretation of effect size depends on the research question. Cohen (1988) defines his effect sizes as: 8 = large (8/10 of a standard deviation unit). 5 = moderate (1/2 of a standard deviation). 2 = small (1/5 of a standard deviation). I would recommend using the "medium" effect size for your project. A medium effect size can range from 0.3 to 0.5.

SAFETY MANAGEMENT

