3 INVESTIGATIONAL PLAN

3.1 General Schema of Study Design

The study will be a randomized 1:1, controlled trial, prospective in nature, where participants undergoing foot and ankle surgery will be randomly placed into one of two

groups; an immediate weight-bearing group or a non-weight-bearing group. The patients will be randomly placed into the study group and control group if they meet all eligibility criteria. The first patient recruited will be assigned a unique study identifier (i.e., FAI001) and a coin flip will randomize the patient into either the study group (Heads) or control group (Tails). From that point, all patients will be placed into their groups by alternating between the control group and the study group. No bias will be placed on the subject or the procedure in regard to inclusion into a certain research group. Patients will be recruited and should they agree will be consented to the study with two year follow up results.

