Descriptive statistics on the physical and mental component scores and the eight subdomain scores from the SF-36 will be reported for the immediate weight-bearing and non-weight bearing groups. In order to examine differences in SF-36 scores within each group over time, a one-way repeated measures ANOVA will be conducted to determine if the SF-36 scores are significantly different between visits (e.g., screening, post-operative at 6-8 weeks, post-operative at 12 months, and post- operative at 24 months). A two-way repeated measures ANOVA will be conducted to determine if the SF-36 scores are significantly be conducted to determine if the SF-36 scores are significantly be conducted to determine if the SF-36 scores are significantly be conducted to determine if the SF-36 scores are significantly be conducted to determine if the SF-36 scores are significantly be conducted to determine if the SF-36 scores are significantly be conducted to determine if the SF-36 scores are significantly be conducted to determine if the SF-36 scores are significantly different between the two groups for these same visits. Post-hoc pairwise comparisons using Tukey's test or Dunn's procedure will be performed, as indicated.

Descriptive statistics on the pain, function and alignment component scores from the AOFAS will be reported for the immediate weight-bearing and non-weight bearing groups. In order to examine differences in AOFAS scores within each group over time, a one-way repeated measures ANOVA will be conducted to determine if the AOFAS scores are significantly different between visits (e.g., screening, post-operative at 6 – 8 weeks, post-operative at 12 months, and post-operative at 24 months). A two-way repeated measures ANOVA will be conducted to determine if the AOFAS scores are significantly different between visits. Post-hoc pairwise comparisons using Tukey's test or Dunn's procedure will be performed, as indicated.

The chi-square test will be used to examine the frequency of complications during the perioperative and post-operative periods, osseous healing as assessed by both clinical and radiographic evaluation and frequency of soft tissue procedures between the immediate weight-bearing and non-weight bearing groups.

Logistic regression analysis will be performed to assess which patient characteristics and surgical characteristics are associated with higher SF-36 scores and AOFAS scores.

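### The 80% power in section 6.5 is for one unadjusted t-test, not for the repeated measures ANOVA with Tukey or Dunn comparisons that section 6.4.1 prescribes for the primary scores

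*Combined protocol and SAP*

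**What the plan says.** Section 6.5 sizes the trial on its primary endpoints, "using an independent-samples t-test with a .05 two-sided significance level" and an "effect size of Cohen's d = 0.40". It concludes that "200 evaluable patients (100 patients in each group) would give you a power of 80% to detect a true difference in means on the questionnaires". It mentions no visit, repeated measurement, covariate or multiplicity correction.

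Section 6.1 makes the AOFAS and SF-36 scores primary, again without a visit. Section 6.4.1 gives both scores a one-way repeated measures ANOVA within each arm and a two-way repeated measures ANOVA. For the SF-36, the two-way model asks whether scores are "significantly different between the two groups for these same visits". For the AOFAS, the matching sentence mentions only differences between visits. The visits are given as examples: screening, 6-8 weeks, 12 months and 24 months. The schedule of procedures and section 7.5 provide for questionnaires at five visits, the fifth being 3 months. Each score paragraph ends: "Post-hoc pairwise comparisons using Tukey's test or Dunn's procedure will be performed, as indicated". The general rule is that "A value of p<.05 on twotailed testing will be considered statistically significant". Section 6.4.1 assigns Student's t-test to demographic and clinical data, and separately says that the scores will be adjusted for age, gender, BMI and diabetes.

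**The concern.** A power statement should describe the test that will answer the primary question. Here the powered test and the written one differ, and the written one leaves open what decides the trial. It could be the ANOVA group term, the group-by-visit term, or an arm contrast at a visit taken from the post-hoc comparisons. These have very different power for the same d = 0.40.

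Tukey's test is an all-pairs method. If it is applied across arm-by-visit cells, most of the pairs it protects do not compare the arms at the same visit, yet they raise the threshold for those that do. The overall group term has a different weakness. It averages screening, 12 months and 24 months with 6-8 weeks, although the regimens differ only in the first 6 weeks.

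The primary objective is similar or superior results. If the deciding test has much less than 80% power, a real difference may go undetected and the result could be taken as similarity. Leaving the deciding test open also allows it to be chosen after the data are seen.

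**Working it through.** **Inputs.** From section 6.5: d = 0.40, 100 evaluable per arm, two-sided .05. From section 3.1: 1:1 allocation. From section 6.4.1: four example visits. From the schedule: five questionnaire visits. Assumed, because the documents give no value: equal variances and one common between-visit correlation ρ, shown for 0.3 to 0.7. Covariate adjustment and the presence of two primary scores are left out.

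**1. The plan's own figure.** Noncentrality = d × √(n/2) = 0.40 × √50 = 2.83. With 198 df the two-sided .05 critical value is 1.97, and the noncentral t gives 80.4% power. The printed 80% is correct for that test.

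**2. The same difference at one visit, as a corrected post-hoc contrast.** The noncentrality stays at 2.83; only the critical value changes. For Dunn, read as Bonferroni, it is the t quantile at .05/m. For Tukey it is the studentized range quantile divided by √2. Pairs among c cells = c(c − 1)/2, so 2 × 4 = 8 cells give 28 pairs and 2 × 5 = 10 cells give 45.

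| Family | Critical value | Power |
|---|---|---|
| One contrast, no correction | 1.97 | 80.4% |
| Dunn, 3 same-visit arm contrasts | 2.41 | 66% |
| Dunn, 4 | 2.52 | 62% |
| Dunn, 5 | 2.60 | 59% |
| Tukey, 8 cells | 3.04 to 3.06 | 41% to 42% |
| Dunn, 28 pairs | 3.17 | 37% |
| Tukey, 10 cells | 3.17 to 3.20 | 36% to 37% |
| Dunn, 45 pairs | 3.31 | 32% |

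The Dunn rows use 198 df; pooled error df add at most about one percentage point. Of the 28 pairs, 4 compare the arms at the same visit, and 1 of those 4 is pre-operative.

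**3. The ANOVA group term** (four visits including screening, 1 and 198 df). Noncentrality = (n/2) × (mean d over visits)² / [(1 + 3ρ)/4].

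- Effect at 6-8 weeks only: mean d = 0.40/4 = 0.10. At ρ = 0.3, 50 × 0.01/0.475 = 1.05, power 17.5%. At ρ = 0.7, 50 × 0.01/0.775 = 0.65, power 12.6%.
- Effect at 6-8 weeks and 12 months: mean d = 0.20, power 53% to 36%.
- Effect at all three post-operative visits: mean d = 0.30, noncentrality 9.47 to 5.81, power 87% to 67%.

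**4. The group-by-visit term** (3 and 594 df). Noncentrality = (n/2) × Σ(d_j − mean d)²/(1 − ρ). An effect at 6-8 weeks only and an effect at all three post-operative visits both give a sum of squares of 0.12. The noncentrality is then 50 × 0.12/0.7 = 8.57 to 50 × 0.12/0.3 = 20, and power is 68% to 97%. This term tests whether the arm profiles have different shapes. If screening is not an outcome visit, a constant post-operative difference leaves the sum of squares at zero and power at the 5% error rate.

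**The case against.** A reader might infer that the trial as written has only 37% to 42% power, about half of what it promises. The documents do not support that. No section defines a family of 28 pairs, the four visits are only examples, and post-hoc tests are said to be done as indicated, not to decide the trial. The 37% end also takes Dunn's procedure to be Bonferroni on means, whereas section 6.4.1 allows nonparametric tests, so a rank-based procedure may be meant.

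Section 6.4.1 also says that the primary analysis focuses on the comparison of the two arms. A two-level group term needs no post-hoc correction. If d = 0.40 is taken on the scale of each patient's average over visits, that term is equivalent to a t-test on those averages and has the same 80.4% power. Nothing in the plan says that the effect is confined to 6-8 weeks. The t-test sentence could be stretched to include the scores as clinical data, and covariate adjustment may add precision that cannot be quantified here.

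All of this stands against a single low figure. It does not restore the 80%. Section 6.5 does not say that d = 0.40 refers to a patient average, the score paragraphs specify the ANOVA, and every multiplicity-corrected arm contrast in the table falls short of 80%. The variety of defensible readings shows that the power of the written analysis is not determined.

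**Conclusion.** The concern holds in a limited form. The 80% is arithmetically right for one unadjusted t-test, which is not the analysis written for the primary scores. The power of the written analysis is undetermined until the deciding visit or term, the comparison family and the within-patient correlation are stated.

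For d = 0.40 and 100 per arm, a corrected arm contrast at one visit has 59% to 66% power for three to five same-visit contrasts, 37% to 42% for all pairs over four visits, and 32% to 37% over five. The group term ranges from about 13% to 87%, depending on how long the effect lasts and on a correlation assumed between 0.3 and 0.7. The interaction term can exceed 80%, but it does not test the difference in means that section 6.5 promises.

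The finding does not show that 230 patients are too few. One pre-specified contrast at .05 has the stated power. The change should be made because it is cheap and makes the printed figure true.

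**What to change.** In section 6.4.1, for SF-36 and AOFAS alike, replace Tukey/Dunn in the between-arm comparison with planned same-visit arm contrasts from the repeated measures model. Before any outcome data are seen, the sponsor names one post-operative visit as primary and tests that arm contrast at two-sided .05. The other post-operative arm contrasts become secondary under Holm. Keep Tukey/Dunn for visit-to-visit comparisons within an arm.

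In section 6.5, state that the 80% at d = 0.40 refers to that one contrast, for each score, before any covariate adjustment.

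If corrected post-hoc tests are kept for the arm comparison, define the family and restate the power for it: about 66% for three post-operative contrasts, or about 37% to 42% for all pairs over four visits.

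The cost is wording in two sections, with no extra patients, visits or data. The small downside is that the other visits become secondary and comparisons of one arm at one visit with the other arm at a different visit are no longer tested.
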